Priming the Brain for Rehabilitation: Brain Stimulation Followed by Constraint-Induced Movement Therapy in Adults with Severe Arm Paresis after Stroke

Study Protocol & Statistical Analysis Plan

NCT03538795

February 12, 2020

[name], Principal Investigator University of Alabama at Birmingham Birmingham, AL 35294

Priming the Brain for Rehabilitation: Brain Stimulation Followed by Constraint-Induced Movement Therapy in Adults with Severe Arm Paresis after Stroke

Outline of Study Design and Procedures

1. Overall Goals

- 1.1. Demonstrate the feasibility of combining intermittent theta burst stimulation (iTBS; a form of TMS) with an expanded form of Constraint-Induced Movement therapy (eCIMT) for treating adults after stroke with chronic, severe upper-extremity impairment.
- 1.2. Get a preliminary read on whether stimulating a brain region that controls movement of the more-affected arm with iTBS boosts the effect of eCIMT on use of the more-affected arm in everyday life and on the motor capacity of that arm.

2. Specific Aims

- 2.1. To gather preliminary data on the therapeutic effect of eCIMT plus iTBS in adults with severe, chronic hemiparesis after stroke. If the data are promising, they will be used to inform decisions about the appropriate sample size and other logistics for a RCT to be proposed to NIH that will compare the efficacy of eCIMT+iTBS to a) eCIMT alone and b) usual care.
- 2.2. To establish feasibility for using magnetic resonance spectroscopy (MRS) to identify the cellular basis of any neuroplastic changes we might observe after eCIMT+iTBS. Our labs already have expertise in magnetic resonance imaging (MRI) methods that will permit detection of changes in brain activity (fMRI) and grey matter (MRI) and white matter structures (diffusion weighted imaging; DWI). If any changes in brain activity or structure take place, MRS will permit examination of the changes in the cellular composition of those regions. As noted, grey and white matter changes have been observed after the original form of CIMT.

3. Study Design

3.1. Baseline Testing→ No treatment for 3 weeks→ Pre-treatment Testing→ eCIMT+iTBS for 3 weeks→ Post-treatment Testing→ 4-weekly follow-up phone calls→ → → 12-month follow-up.

4. Participants

- 4.1. Twenty adults more than 1-year after stroke with severe impairment of their more-affected arm, i.e., plegic or nearly plegic hands

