 - 5.5.8.eCIMT- Transfer Package component (assignment of home skill assignment, etc...; 5-10 min typically but substantially longer on first day)
 - 5.5.9. eCIMT- padded safety mitt will be worn on less-affected to discourage its use both during treatment and at home. Time that mitt is worn will be determined by safety considerations and the degree to which the patient needs to use the less-affected arm to accomplish tasks that are typically bilateral.
 - 5.5.10. eCIMT- splinting and orthotic devices will introduced during eCIMT sessions on an as needed basis to support use of the more-affected arm to complete tasks.

6. Motor Function Testing

- 6.1. Occasions: Baseline, Pre-treatment, Post-treatment, 12-month follow-up
- 6.2. Setting: Taub Therapy Clinic and Blinded Testing Room ("Pink Room," SRC R056). Grade 4/5 WMFT will be conducted in Pink Room to permit collection of kinematic data.
- 6.3. Tests
 - 6.3.1. Grade 4/5 Motor Activity Log (everyday use of more-affected arm)
 - 6.3.2. Canadian Occupational Performance Measure (everyday use of arms)
 - 6.3.3. Grade 4/5 Wolf Motor Function Test (motor capacity of that arm)

7. Data Analysis

- 7.1. Primary outcome is change from baseline to post-treatment on MAL
- 7.2. If the enrollment target is met, a repeated measures ANOVA will be used to evaluate whether statistically significant improvement is present on the primary outcome. The repeated measures factor will be Testing Occasion (baseline, pre-treatment, post-treatment, 12-month follow-up). If the omnibus test is significant, specific contrast statements will be used to test when improvement takes place.

- 7.3. Parallel methods will be used to evaluate the secondary outcomes.
- 7.4. If the sample size is substantially smaller than projected, changes on the primary outcome will be characterized using descriptive statistics.

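### The omnibus F over four occasions is the only stated protection for unnamed follow-up contrasts; it does not hold the error rate at 5% once one occasion differs, and it costs the primary comparison power

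*Combined protocol and SAP*

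**What the plan says.** Section 7.1 names one primary comparison: "Primary outcome is change from baseline to post-treatment on MAL". Section 7.2, which applies if the enrollment target is met, uses a repeated measures ANOVA to "evaluate whether statistically significant improvement is present on the primary outcome". The repeated factor has four levels: baseline, pre-treatment, post-treatment and 12-month follow-up. It then adds: "If the omnibus test is significant", "specific contrast statements will be used to test when improvement takes place".

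Section 7.3 extends the approach: "Parallel methods will be used to evaluate the secondary outcomes". Section 7.4 falls back on descriptive statistics for the primary outcome if the sample is substantially smaller than projected.

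The plan does not list the contrasts. It gives no significance level or sidedness, names no error term, and neither adopts nor rules out a multiplicity adjustment. Section 7.2 does not say that the 7.1 comparison is one of the contrasts.

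**The concern.** Making the contrasts wait for a significant omnibus test shows an intent to limit false positives. With four means, that works only under the complete null. One real change is enough to open the gate, and each contrast that is still truly null is then tested at its full level. With the set unnamed, up to six pairs are available and could be chosen after the data are seen.

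The contrasts left exposed matter here. The design in 3.1 has no control group. Baseline to pre-treatment is the only internal check on change without treatment, and post-treatment to 12 months is the retention result. If treatment works and the gain lasts, these are the two truly null contrasts. A false drift or a false loss would misstate when change happened, in data that 2.1 intends for planning an RCT.

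There is also a cost in the other direction. As written, the 7.1 comparison, if it is among the contrasts, is reached only through an omnibus test that spreads its sensitivity over three degrees of freedom.

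**Working it through.** The plan states no error rate or power, so there is no figure of its own to reproduce.

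**Inputs from the documents.** Four occasions (7.2), giving 4 × 3 / 2 = 6 pairs, 3 adjacent pairs, or 3 comparisons with baseline. Sample size 20 (4.1: "Twenty adults more than 1-year after stroke with severe impairment of their more-affected arm"). The omnibus gate (7.2).

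**Assumptions.** Two-sided 0.05 for the F test and for each contrast; no adjustment; no dropout; paired error terms unless stated. Within-person correlation is either compound symmetry at 0.7 or decaying with time. Shifts are in units of the between-person SD at one occasion.

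**Step 1, by hand.** If the gate is open and k independent null contrasts are each tested at 0.05, the chance of at least one false result is 1 − 0.95^k.
- k = 2: 1 − 0.9025 = 9.75%.
- k = 3: 1 − 0.8574 = 14.3%.

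Under compound symmetry, baseline to pre-treatment and post-treatment to 12 months are uncorrelated (ρ − ρ − ρ + ρ = 0), so k = 2 fits the retained-gain case. The three pairs among three equal means are correlated, so their rate must lie below 14.3%.

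**Step 2, simulation.** 40,000 trials per setting, with a 2 SD shift where there is one:

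| True pattern | Contrasts tested | Truly null | Any false contrast |
|---|---|---|---|
| No occasion differs | any set | all | 3.9-5.3% |
| Baseline = pre, post = 12-month | all six or adjacent | 2 | 9.6-10.0% |
| Same | versus baseline | 1 | about 5% |
| Only post differs | all six | 3 | 12.0-12.5% |
| Only post differs | versus baseline | 2 | about 9% |
| Only post differs | adjacent | 1 | about 5% |
| Partial retention (post +2, 12-month +1) | all six | 1 | about 5% |

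The first row rises to about 7% if correlation decays with time and the F test is not corrected for non-sphericity. The 12% row becomes 11.3-12.2% under decaying correlation.

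**Step 3, smaller effects.** At a 0.5 SD shift under compound symmetry, the gate opens in 93% of trials (gain kept) or 83% (only post differs). The rates are then about 9.7% and 11.9% with all six pairs. With decaying correlation and a Greenhouse-Geisser corrected gate they can fall to 8.1% and 9.6%.

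**Step 4, direction.** Counting only false improvements gives 4.9-5.1% for the retained-gain pattern and 5.8-6.8% for one differing occasion with all six pairs.

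**Step 5, error term.** With the pooled ANOVA error and decaying correlation, the retained-gain rate is about 13%. The three-equal-means rate ranges from 0.4% to 17.7%. Holm adjustment with that pooled term still reaches about 8-9%, so the error term needs stating as well.

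**Step 6, primary comparison.** Take a 0.4 SD change with correlation 0.7. The standardized paired change is 0.4 / √(2 × 0.3) = 0.516, and 0.516 × √20 = 2.31 against a critical t of 2.093 on 19 degrees of freedom. Tested directly, power is 0.59. When the omnibus test must also be significant, it is 0.48-0.54, depending on the 12-month mean.

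**Step 7, the alternative.** Testing baseline to post-treatment first, then Holm on the supporting contrasts with paired error terms, kept false positives at about 5% or less in every setting run, with two or three supporting contrasts. Power of a supporting contrast at a standardized change of 0.66 (0.66 × √20 = 2.95):
- at 0.05 (critical t 2.093): 80%
- at 0.025, first Holm step of two (2.433): 70%
- at 0.0167, first Holm step of three (2.625): 63%

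**The case against.** The case for leaving the plan alone is a serious one.

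- **The plan never says the contrasts are unadjusted.** That stands. It is silent, and the rates above hold only if the silence means no adjustment.
- **A reader might infer that false claims of improvement occur in 10-13% of such trials.** The documents do not support that. The higher rates need two or three truly null contrasts in the tested set. They also count declines as well as gains. Partial retention, a set limited to comparisons with baseline under a sustained gain, or no change at all each bring the rate back to about 5%. Counting declines is still reasonable for drift and retention, where a false fall misleads as much as a false rise.
- **Naming fewer contrasts may do the work, not Holm.** This is right for the only-post pattern, where three adjacent contrasts without adjustment already give about 5%. It is not right for the retained-gain pattern, where adjacent contrasts without adjustment give about 10%.
- **Adjustment makes real drift or real loss easier to miss.** This stands, and it is the reason to report unadjusted confidence intervals whatever the tests show.
- **The study is preliminary, with one named primary comparison.** Sections 1.1, 1.2 and 2.1 say so. That limits the weight of the point. It does not remove it, because 7.2 commits to significance tests and puts the primary comparison behind the gate.

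**Conclusion.** The point holds as a weakness of method and specification that should be corrected. It does not invalidate the primary comparison. The omnibus gate gives real protection only when no occasion differs; where one null contrast remains, the 5% comes from that contrast's own level. For the outcome the trial hopes for (stable before treatment, improved after, gain kept), the rate of any false contrast is about 10% with all or adjacent pairs. The 12% figure needs all six pairs and a 12-month mean back at baseline.

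These sizes rest on an assumed two-sided 0.05, no adjustment, 20 complete participants and assumed correlations; the plan states none of these except the sample size. Because the contrast set is unnamed, the plan cannot show that it falls in a case where the rate stays near 5%. The loss of primary power from the gate (0.59 to 0.48-0.54 in the example) is a second reason to change the rule.

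**What to change.** Replace the last sentence of 7.2 with a rule to this effect:

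1. The baseline to post-treatment contrast on the MAL is tested first, at two-sided 0.05, with a paired error term and without regard to the omnibus result. The omnibus F is reported as supportive.
2. If that contrast is significant, a named supporting set is tested with Holm adjustment and paired error terms: baseline to pre-treatment, post-treatment to 12-month and, if wanted, pre-treatment to post-treatment (the treatment interval itself).
3. Unadjusted 95% confidence intervals are reported for every contrast whatever the tests show. A non-significant baseline to pre-treatment or post-treatment to 12-month result is not read as proof of no drift or no loss.

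Bring the opening sentence of 7.2, which gives the ANOVA the job of judging improvement, into line with step 1. Apply the same named set to each outcome under 7.3, and say that error is controlled within each outcome, not across them.

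The change is to wording only. At a standardized change of 0.66, a supporting contrast drops from about 80% power to 70% at the first Holm step with two contrasts, or 63% with three. The primary contrast loses no power, and gains some compared with the gated rule.

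### The primary MAL change gets its own analysis only after a significant four-occasion omnibus test; it should be estimated with a 95% CI whatever that test shows and whatever the final n

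*Combined protocol and SAP*

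**What the plan says.** The combined protocol and SAP sets out the analysis in four short items.

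- Section 7.1: "Primary outcome is change from baseline to post-treatment on MAL". Section 6.3.1 identifies the instrument as the Grade 4/5 Motor Activity Log.
- Section 7.2: "If the enrollment target is met, a repeated measures ANOVA will be used", as a test for statistically significant improvement. The repeated factor has four levels: baseline, pre-treatment, post-treatment and 12-month follow-up. Then: "If the omnibus test is significant, specific contrast statements will be used to test when improvement takes place".
- Section 7.3: "Parallel methods will be used to evaluate the secondary outcomes".
- Section 7.4: "If the sample size is substantially smaller than projected, changes on the primary outcome will be characterized using descriptive statistics". No statistic is named.

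Section 4.1 sets enrolment at 20, and section 3.1 describes a single-arm sequence. Goal 1.2 seeks a preliminary indication of benefit. Under Aim 2.1, if the data are promising, "they will be used to inform decisions about the appropriate sample size and other logistics for a RCT" that would "compare the efficacy of eCIMT+iTBS to a) eCIMT alone and b) usual care".

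**The concern.** The declared outcome and the declared test do not match. The outcome is one difference between two visits. The test asks whether any of four occasion means differ. It can be significant because of the 12-month visit, and it can miss a real baseline-to-post-treatment change because that change is pooled with other comparisons.

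The contrast that would address the primary outcome sits behind this gate, and is described as a test rather than an estimate. So a non-significant omnibus result ends the planned inference with nothing required on the primary change. If the change is quantified only when the omnibus is significant, the reported values are a selected, upward-biased set.

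Both consequences bear on the study's purpose. A preliminary reading of the effect, and planning of a later trial, need the size of the change and its uncertainty whichever way the test falls.

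**Working it through.** **What the plan requires for the primary change**

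| Situation | Required by the plan |
|---|---|
| Target met, omnibus significant | Contrasts, as tests |
| Target met, omnibus not significant | Nothing specific to baseline to post-treatment |
| Sample well below 20 | Descriptive statistics, unnamed; no interval |
| Sample slightly below 20 | Not assigned to either section |

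The target of 20 cannot be reproduced: no alpha, power, effect size, SD or dropout rate is given. The figures below show scale only.

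**Assumptions (none is in the documents).** Alpha 0.05; normal scores with equal SD σ at each occasion; compound symmetry with correlation ρ = 0.5; no missing data; no change before treatment. The SD of change is σ√(2(1−ρ)) = σ, so here a change in SDs of a single score equals the same number of SDs of change.

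**Step 1: how often the gate stays shut at n=20.** The omnibus F has 3 and 3×19 = 57 df, with critical value 2.766. Its noncentrality is λ = n·Σ(μj − μ̄)² / [σ²(1−ρ)].

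For a true change of 0.5 SD:
- Gain kept, means (0, 0, 0.5, 0.5): Σ = 4×0.25² = 0.25, so λ = 20×0.25/0.5 = 10. Power 0.729; not significant in 27.1%.
- Gain lost, means (0, 0, 0.5, 0): Σ = 3×0.125² + 0.375² = 0.1875, so λ = 20×0.1875/0.5 = 7.5. Power 0.590; not significant in 41.0%.

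The same steps for other sizes:

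| True change | Pattern | λ | Omnibus significant | Not significant |
|---|---|---|---|---|
| 0.3 SD | kept | 3.6 | 30.5% | 69.5% |
| 0.3 SD | lost | 2.7 | 23.5% | 76.5% |
| 0.5 SD | kept | 10.0 | 72.9% | 27.1% |
| 0.5 SD | lost | 7.5 | 59.0% | 41.0% |
| 0.8 SD | kept | 25.6 | 99.1% | 0.9% |
| 0.8 SD | lost | 19.2 | 95.8% | 4.2% |

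**Step 2: bias if change is reported only after significance.** Simulation, 200,000 trials per scenario. Mean observed baseline-to-post-treatment change among trials with a significant omnibus:
- true 0.3 SD: 0.45 (kept), 0.50 (lost);
- true 0.5 SD: 0.57 (kept), 0.61 (lost);
- true 0.8 SD: 0.80 (kept), 0.82 (lost).

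**Step 3: width of the missing interval.** The 95% half-width is t(0.975, n−1)/√n, in SDs of change:
- n=20: 2.093/4.472 = 0.47
- n=15: 2.145/3.873 = 0.55
- n=10: 2.262/3.162 = 0.72

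**The case against.** The best defence is that this is an outline for a 20-person feasibility study. It does not forbid estimates, ANOVA or contrast output could supply them, and descriptive statistics for a continuous score would ordinarily include a mean and SD. With n, those give the interval. This stands in part. It means the section 7.4 branch is the less exposed one, and that the defect is an omission, not a contradiction. It does not answer section 7.2, where the stated rule makes the only primary-specific analysis conditional on a test of something broader.

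A reader might infer that the omnibus test wastes power. The figures do not show that. At a true 0.5 SD, a paired t-test of the primary change is significant in about 56% to 57% of simulated trials, against 73% or 59% for the omnibus. The objection is to the gate and the missing estimate, not to power.

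A reader might also infer that the omission puts the later trial's size in doubt by a multiple. At n=20 the 95% chi-square interval for a variance runs from 0.58 to 2.13 times the estimate, and a sample size based on it would scale likewise if the target difference were fixed. But that is sampling error of an SD from 20 people, the same whether or not an interval is printed. Aim 2.1 says only that the data will inform sizing. These multiples do not measure harm from the omission.

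**Conclusion.** The point holds as a mismatch between the primary outcome and its analysis, with a conditional step that can leave the outcome unanalysed. The reading of sections 7.1, 7.2 and 7.4 needs no assumptions; its size does. At n=20, with alpha 0.05 and correlation 0.5, a true change of 0.5 SD leaves no primary-specific analysis in about 27% to 41% of trials. A true 0.3 SD reported only after significance averages about 0.45 to 0.50 SD. If the true change is near 0.8 SD, the gate opens in about 96% to 99% of trials and the bias is negligible. The documents do not indicate which case applies.

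The documents do not support going further and requiring a confidence interval for the SD. It can be derived from n and the SD, and it is fragile: in simulation at n=20 a nominal 95% chi-square interval covered 73% for an assumed skewness of 2. It is optional and approximate. The unassigned range just under 20 is a wording point only.

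**What to change.** In sections 7.2 and 7.4, state that the primary analysis is the mean baseline-to-post-treatment MAL change, reported with its SD, n and t-based 95% CI for all participants with both visits, at any final n and whatever the omnibus result. Keep the four-occasion ANOVA and its contrasts as supporting analyses of when change occurs. Through section 7.3, report the secondary outcomes in the same way.

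Add one sentence saying that this single-arm change does not estimate the between-arm difference in the later RCT.

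As a minor edit, make the conditions in sections 7.2 and 7.4 complementary, so that every final sample size falls under exactly one of them, and say which count of participants applies.

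The cost is a few sentences and no extra data. The downsides are that the interval will be wide at small n (half-width 0.47 SD of change at n=20, 0.72 at n=10) and that it relies on approximate normality. In simulation at n=20, coverage of the t-interval was 94% for an assumed skewness of 1 and 92% for 2.
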